#### Characteristics of the Research Population

##### II.a. Number of Subjects

Total Number of Subjects in Home Visit and Usual Care arms: 85

Number of Subjects in Home Visit Arm: 25 subjects with Progressive supranuclear palsy, multiple system atrophy, corticobasal syndrome, or atypical parkinsonism. Participation in the home visit arm neither requires nor prohibits participation in the survey pilot phase.

Number of Subjects in Usual Care Arm: 60 subjects with Progressive supranuclear palsy, multiple system atrophy, corticobasal syndrome, or non-idiopathic PD atypical parkinsonism. Participation in the usual care arm neither requires nor prohibits participation in the survey pilot phase.

This is an exploratory study; no power analysis was conducted. The number of home visit subjects was projected based on recruitment to pilot work at NYU and discussions with Rush colleagues regarding feasibility. The number of control subjects was based on discussions with CurePSP senior staff regarding the size of their support group and social media-connected networks.

##### II.b. Gender of Subjects

There will be no exclusion of subjects based on gender.

##### II.c. Age of Subjects

Subjects will be 40 years of age and older.

##### II.d. Racial and Ethnic Origin

There will be no exclusion of subjects based on racial or ethnic characteristics. Study demographics are expected to match those of the population from which it was drawn. However, subjects must be fluent in English to participate in the Home Visit Program due to the general lack of appropriately translated

neurological and neuropsychological assessments and appropriate normative comparison samples. These factors are critical for accurate administration, scoring, and interpretation of neurological and neuropsychological test data.

II.e. Inclusion Criteria for All Subjects:

1. Each subject must be 40 years of age or older. A subject may be of either gender, any race/ethnicity.
2. Subjects will be those diagnosed with progressive supranuclear palsy, multiple system atrophy, corticobasal syndrome, Dementia with Lewy Bodies (DLB), or atypical parkinsonism without mention of idiopathic Parkinson's disease.
3. English speaking.

a. **Additional Inclusion Criteria For Home Visit Arm:**

- i. Each subject must *either* 1) be willing and able to provide written, informed consent for the study, and for whom capacity to consent will be assessed using the "Additional Inclusion Criteria for Home Visit Arm" document, or 2) if unable to provide informed consent due to lack of capacity, a caregiver is able to provide informed consent *and* the subject provides assent to participation.
- ii. Subjects must be homebound according to the Medicare definition: "Leaving your home isn't recommended because of your condition; your condition keeps you from leaving home without help (such as using a wheelchair or walker, needing special transportation, or getting help from another person); leaving home takes a considerable and taxing effort." (<http://www.medicare.gov/pubs/pdf/10969.pdf>)
- iii. Subjects reside in Chicago at the time of Visit 1.
- iv. The Subject must reside independently at the time of Visit 1.
- v. Subjects have one or more of the following criteria:
  - Fluctuation
  - Multi-morbidity
  - Mismanages medication
  - Cognitive impairment
  - Symptoms of depression and/or anxiety
  - High risk for re-hospitalization
  - High risk for nursing facility admission
  - Suspected elder abuse
  - Recent history of increased falls in home
  - Caregiver burnout suspected
- vi. Ability to participate in the research study as deemed by the Principal Investigator.

b. **Additional Inclusion Criteria for Usual Care Arm:**

- a. Independent access to an internet-connected computer in order to complete online survey
- b. Valid email address

- c. Each subject must review and acknowledge their ability to provide informed consent for the study via the first screen of the online survey.

#### II.f. Exclusion Criteria for All Subjects

1. Diagnosis of idiopathic Parkinson's Disease
2. Diagnosis of another neurodegenerative disease (e.g., amyotrophic lateral sclerosis, frontotemporal dementia)
3. Subjects with active psychosis or exhibiting symptoms of a severe psychiatric disorder.

II.g. Vulnerable Subjects – This study will not include children, prisoners, and homeless persons. The consent form will state that participation in our study will **not** affect their clinical care. These subjects will be evaluated by clinicians (neurologist—either movement disorders attending or fellow; social worker; nurse) trained in evaluating and treating subjects with cognitive impairments. Cognition is impacted by Progressive Supranuclear Palsy, Corticobasal Degeneration, and Dementia with Lewy Bodies, with increasing prevalence of cognitive impairment over time, and thus the homebound, advanced PRD population suffers from a high burden of cognitive decline. Therefore, it is important to include patients with and without cognitive impairment to understand possible treatment and care options for this population and for the results of our study to be generalizable to the broader advanced PD population.

### III. Methods and Procedures

#### Study Visits

**Home Visit Subjects:** The study team will screen clinical records and review physician-referred patients. They will contact potential patients or patient-caregiver dyads to review the study objectives, eligibility criteria, and scheduling.

At Visit 1, the nurse, social worker, and a member of the research team will travel to the home. The neurologist may be present in person or via telemedicine. If the neurologist is present via telemedicine, the home visit team will travel with an iPad and, after obtaining informed consent, connect to the neurologist via HIPAA-secure videoconferencing and begin the protocol-driven clinical activities and assessments in Figure 1. The nurse will conduct and, with the neurologist, score the UPDRS Motor Examination, reconcile medications, and complete a standardized home safety assessment. The social worker will obtain demographics, and administer the Multidimensional Caregiver Strain Index (MCSI) to the caregiver and the EuroQoL-5D (EQ5D) to both the patient and caregiver, respectively. The social worker will conduct a needs assessment of the dyad, including a discussion of goals of care. The team will administer the same survey that the usual care subjects will complete as a structured interview, as individuals in the home visit arm are expected to have more difficulty with dexterity and potentially cognitive issues, limiting the feasibility of completing the online survey unassisted. The survey will cover demographics, disease history, comorbidities, healthcare utilization, and unmet needs of the patient and caregiver. The team will probe for further details on necessary services or resources, and will ask specifically about areas of need in: education, resources, non-motor symptoms, psychiatric and palliative care, spiritual and/or religious support, and end-of-life planning. The team will create and counsel the dyad on a care plan. Within the Rush electronic medical record, the neurologist will enter

orders and send a comprehensive, template-based note to the patient's healthcare providers.

Visits 2-4 will be conducted at 4-month intervals and are identical except the social worker may also join either in person or by telemedicine, depending on availability, and the queries on unmet needs will only be repeated at Visit 4. The visits may be performed where the subject is residing at the time of scheduled visit (which could include but not restricted to the subject's home, nursing facility, hospital, etc.). The duration of the visits will be approximately 1.5-2 hours.

If, in the course of any of the home visits, or in the course of any post-visit follow-up either initiated by the subject, caregiver (if applicable), or the study team, any member of the study team suspects adult abuse or that the subject is of imminent danger to themselves or others, that study team member will discuss those concerns with the study nurse, physician, and social worker either immediately at the time the concern arises (in the case of concerns arising during a home visit, as detailed below), or as soon as that discussion is feasible, in the case of a follow-up phone call or other contact.

If there is an immediate concern during a home visit and the study team member feels uncomfortable or unsafe raising the concern in front of the subject and/or caregiver, all team members will be trained in the following "time-out" procedure: Any team member may use the phrase, "**I think that the team needs to step outside for a moment**", at which time all team members will acknowledge this and safely exit the subject's home either into a hallway (for apartments or condominiums) or outdoors (for independent dwellings). If the team is connected to the physician by telemedicine at that time, the team will bring the iPad with them. If the team is not connected at that time, they will connect with the physician before proceeding with the discussion. The concerned team member will describe their concern, solicit additional input from other team members, and if *any one* of the mandated reporters—nurse, social worker, or physician—agree that there is sufficient evidence for concern, the team will devise an intervention strategy. If there is a concern for adult abuse—including physical abuse, sexual abuse, emotional abuse, confinement, passive neglect, willful deprivation, or financial exploitation—the team social worker will be responsible for contacting Adult Protective Services (APS) to report the suspected abuse, neglect, or exploitation at [name], and for notifying the subject and/or caregiver of this report. If the team feels that disclosing this intent to report in the presence of the subject and/or caregiver would pose additional risk to the subject and/or study team, the team will conscientiously express their concerns to the subject and/or caregiver upon re-entering the home, but may defer specific discussion of the impending APS report for safety purposes. The team social worker will be responsible for contacting APS within 1 business day of the visit, documenting this in the electronic medical record, and routing this documentation to the remainder of the study team. Similarly, the social worker will be responsible for following up on and notifying the team of the outcome of the APS referrals in a timely fashion.

In the event that a subject or caregiver is felt to be an imminent danger to themselves, the team will use the procedure above *except* that the research assistant will remain with the subject and/or caregiver for safety purposes while the remainder of the team convenes outside of the home to discuss the concern. If any one of the nurse, social worker, or physician agree that there is sufficient concern for suicide risk, the nurse will contact 911, the social worker (and physician via telemedicine) will rejoin the subject/caregiver and research assistant, and all will remain with the individual(s) until emergency medical personnel arrive. The team will let the subject/caregiver know about their concerns and the 911 call, and will provide supportive counseling while awaiting the arrival of emergency medical personnel and transport of the concerning individual to the nearest appropriate medical facility.

**Usual care/controls:** Control subjects, and caregivers if available, will each complete an online survey querying the same demographic, diagnostic, disease history, needs, resource utilization questions, and the EQ5D. If the control subject indicates that she or he has an available and willing caregiver, the subject will be prompted to have their caregiver complete the caregiver portion of the survey once the subject has completed his portion. Control subjects will be contacted 12 months following the initial survey to complete a follow-up survey. Control participants and CurePSP support group leaders will be reminded to complete the survey; the study team will then email all control subjects with incomplete surveys one week after the initial email and with up to 3 email reminders to maximize response rate.

**Assessments:** Home visit subjects who agree to be part of the study and sign the Informed Consent Form will be asked to complete a series of neurological and neuropsychological assessments to assess their current neurological status, intellectual functioning, memory, and mood. There is no known risk associated with participation in these assessments, and they are a part of routine clinical care for these conditions. These tests can be cognitively demanding but are typically experienced as interesting to subjects. Administration of these assessments should take approximately two hours. All study assessments are specified in Appendix A, in the Schedule of Events table. All or some of the following neurological assessments and self-report measures may be administered but are not limited to:

- *Unified Parkinson's Disease Rating Scale (UPDRS):* A rating scale used to follow the longitudinal course of Parkinson's disease, applicable to PRD
- *Hoehn and Yahr Scale (HY):* A system used for describing how Parkinson's symptoms progress and the relative level of disability. There are five stages: Stage 0 – No signs of disease; Stage 1 – Unilateral disease; Stage 1.5 – Unilateral plus axial involvement; Stage 2 – Bilateral disease, without impairment of balance; Stage 2.5 – Mild bilateral disease with recovery on pull test; Stage 3 – Mild to moderate bilateral disease; some postural instability; physically independent; Stage 4 – Severe disability; still able to walk or stand unassisted; Stage 5 – Wheelchair bound or bedridden unless aided.
- *Montreal Cognitive Assessment (MoCA) and abbreviated versions of the MoCA:* a brief 30-point questionnaire test that is used to screen for cognitive impairment and has been extensively validated in PD; also used to estimate the severity of cognitive impairment at a specific time and to follow the course of cognitive changes in an individual over time, thus making it an effective way to document an individual's response to treatment. Any score greater than or equal to 24 points (out of 30) is effectively normal (intact). The raw score may also need to be corrected for educational attainment (additional 1 point added to total score if  $\leq 12$  years of education).
- *Euro-Qol 5D (EQ5D):* a brief, extensively validated, 6-item instrument measuring five specific domains of health-related quality of life (mobility, self-care, activities of daily living, anxiety/depression, pain/discomfort) and overall well-being. This instrument has been validated for use as a self-administered survey in paper and online via the REDCap software package, as well as having been validated for use with the assistance of an interviewer.
- *Multidimensional Caregiver Strain Index (MCSI):* A validated 18-item tool measuring 6 dimensions of subjective response to stressors. Subscales include physical strain, social constraints, financial strain, time constraints, interpersonal strain, and elder demanding/manipulative. Respondents are asked about the frequency with which items apply, ranging from "never" to "all of the time" on a 5 point scale.

- *Client Satisfaction Inventory – Short Form (CSI-SF)*: A validated, 9-item instrument developed within the field of social work to assess client satisfaction with multidisciplinary programs. Each item consists of a statement in the first-person, and subjects respond on a 7-point Likert scale to indicate their satisfaction with usual care at baseline, and with the HVP at Visit 4. One copy each will be provided to the subject and the caregiver (if present).

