Subjects who commence on study will receive four quarterly structured, interdisciplinary home visits over 12 months from a team comprised of a movement disorders neurologist, social worker and nurse. At Visit 1, the nurse, social worker, and a member of the research team will travel to the home. The neurologist will be present via telemedicine. The home visit team will travel with an iPad and, after obtaining informed consent, connect to the neurologist via HIPAA-secure videoconferencing and begin the protocol-driven clinical activities and assessments in Figure 1 in the uploaded protocol. The nurse will conduct and, with the neurologist, score the UPDRS Motor Examination, reconcile medications, and complete a standardized home safety assessment. The social worker will obtain demographics, and administer the Multidimensional Caregiver Strain Index (MCSI) to the caregiver and the EuroQoL-5D (EQ5D) to both the patient and caregiver, respectively. The social worker will conduct a needs assessment of the dyad, including a discussion of goals of care. The team will administer the same survey that the usual care subjects will complete as a structured interview, as individuals in the home visit arm are expected to have more difficulty with dexterity and potentially cognitive issues, limiting the feasibility of completing the online survey unassisted. The survey will cover demographics, disease history, comorbidities, healthcare utilization, and unmet needs of the patient and caregiver. The team will probe for further details on necessary services or resources, and will ask specifically about areas of need in: education, resources, non-motor symptoms, psychiatric and palliative care, spiritual and/or religious support, and end-of-life planning. The team will create and counsel the dyad on a care plan. Within the Rush electronic medical record, the neurologist will enter orders and send a comprehensive, template-based note to the patient's healthcare providers. Visits 2-4 will be conducted at 4-month intervals and are identical except the social worker may join by telemedicine, depending on availability, and the queries on unmet needs will only be repeated at Visit 4.

The visits may be performed where the subject is residing at the time of scheduled visit (which could include but not restricted to the subject's home, nursing facility, hospital, etc.). The duration of the visits will be approximately 2.5-3 hours for Visit 1 and 1.5-2 hours for Visits 2-4.

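### The treating team asks the primary scales in the home-visit arm while controls answer online, so reporting may drift in one arm only and bias the 1-year change, by an unknown amount and in an unknown direction

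*Protocol*

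**What the plan says.** **Home-visit arm.** Protocol I.c and III (Study Visits) have the social worker at Visit 1 "administer the Multidimensional Caregiver Strain Index (MCSI) to the caregiver" and the EQ5D to both members of the dyad. The social worker also does the needs assessment and the goals-of-care discussion. The shared survey is given by interview: "The team will administer the same survey that the usual care subjects will complete as a structured interview". The reason offered is "as individuals in the home visit arm are expected to have more difficulty with dexterity and potentially cognitive issues". The same team delivers the intervention: "The team will create and counsel the dyad on a care plan".

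**Later visits.** The program is "four quarterly structured, interdisciplinary home visits over 12 months from a team comprised of a movement disorders neurologist, social worker and nurse", with a follow-up call planned after each visit. Section III describes Visits 2-4 as the same as Visit 1, except that the social worker may attend in person or remotely and the unmet-needs questions return only at Visit 4. Appendix A marks the MCSI and EQ5D as in-person at all four visits without naming a role. It marks the social worker's psychosocial assessment as telehealth from Visit 2 on.

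**Control arm.** "Control subjects, and caregivers if available, will each complete an online survey", repeated once at 12 months.

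**Scales and analysis.** For the EQ5D, the Assessments section describes self-administered use on paper and online as validated, "as well as having been validated for use with the assistance of an interviewer". It says nothing comparable about any mode for the MCSI. The SAP lists both scales under primary outcomes and compares 1-year change between groups, with treatment status as the main regressor. No common mode, assessor outside the treating team, mode variable or related sensitivity analysis appears in either document.

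**The concern.** Both scales are subjective. How people answer can depend on who asks and on what that person has done for them. At Visit 1 the team has not yet delivered the program. By Visit 4 it has made three earlier visits and the planned calls, and it is asking about the result of its own work. Controls answer the same kind of online form at both time points.

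A mode effect that stays constant cancels in a change score. One that moves with exposure to the program does not. It would enter the estimated program effect on quality of life and caregiver strain directly. Because every home-visit participant is on one side of the mode divide and every control on the other, a covariate for mode would be the treatment indicator itself.

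The stated reason for interviewing concerns patients' dexterity and cognition. It gives no reason for a clinician to put the MCSI to caregivers.

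**Working it through.** **1. The plan's own figure.** The SAP gives 42-63 patients for a VAS difference of 8.0-6.5, with SD 18, power 0.80 and two-sided alpha 0.05. The one-sample normal formula n = (18 × (1.960 + 0.842) / d)² gives 39.7 for d = 8.0 and 60.2 for d = 6.5. The one-sample t-test version gives 42 and 63, an exact match. The stated range is therefore a within-group calculation. It has no bearing on this point beyond supplying the SD.

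**2. Who asks, and how, at each time point.**

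| | Baseline | 1 year |
|---|---|---|
| Home visit | Social worker in the home; program not yet delivered | Treating team after three earlier visits and the planned calls; asker not named in Appendix A, social worker marked telehealth |
| Control | Online, no clinician | Online, no clinician |

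The control row does not change and the home-visit row does. This holds whether the social worker or the nurse asks at Visit 4, since both belong to the treating team.

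**3. What a drift would do to the test (illustration).** Inputs:
- Arm sizes: 17 v 80 patients at 12 months (SAP: 20 × 0.85 and 100 × 0.80), and 25 v 60 (Protocol II.a, before dropout).
- SD of change: 18. The SAP states 18 without saying it is the SD of change, so using it this way is an assumption.
- Drift b: 3-5 VAS points in the home-visit arm only, with no true effect. This is an assumption; the documents give no mode effect.

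SE = 18 × √(1/nT + 1/nC)
- 17 v 80: 18 × √(1/17 + 1/80) = 4.81
- 25 v 60: 18 × √(1/25 + 1/60) = 4.28

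The rejection probability of a two-sided 5% pooled t-test is taken from the noncentral t distribution with noncentrality b/SE:

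| Arms | b | b/SE | Two-sided rejection |
|---|---|---|---|
| 17 v 80 | 0 | 0 | 5% |
| 17 v 80 | 3 | 0.62 | 9% |
| 17 v 80 | 5 | 1.04 | 18% |
| 25 v 60 | 0 | 0 | 5% |
| 25 v 60 | 3 | 0.70 | 11% |
| 25 v 60 | 5 | 1.17 | 21% |

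The two-sided rate is the same for a drift of either sign. A drift toward better scores mimics benefit; a drift toward worse scores mimics harm or hides benefit. By the normal approximation, power at 17 v 80 for a true 6.5-8.0 point difference is only 27-38%, so an artifact of a few points is not small next to the signal.

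**4. MCSI.** The documents give no SD of change, no target difference and no count of home-visit caregivers. No error rate can be derived for it.

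**The case against.** The strongest reply is that mode is constant within each arm and so cancels in change. That is right for any fixed mode effect, and it disposes of part of the concern. It does not cover the change in the respondent's relationship to the team between Visit 1 and Visit 4.

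Several stronger readings are tempting, but the documents do not support them:
- **That the bias favors the program.** Nothing shows this. Caregivers guarded with a stranger at Visit 1 may disclose more strain once they trust the team, which would count against the program.
- **That one increasingly familiar social worker asks at every visit.** The sentence naming the social worker describes Visit 1. Section III and Appendix A leave the asker at Visits 2-4 open, and no text says the same person attends throughout.
- **That controls answer in private.** They answer online without a clinician. No privacy is required in either arm, and the control subject prompts the caregiver.
- **That even a constant mode difference biases the result because levels at 1 year are compared.** Protocol I.a does speak of 1-year levels, but as measured by change, and the SAP's between-group analyses are of change.
- **That the MCSI is validated for self-completion but not for interview.** The protocol supports no particular mode for it. The case for online completion is that both arms would then share a mode.

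Two further points stand. The illustration ignores the planned stratification by diagnosis. Carrying the last value forward would replace some Visit 4 scores with earlier ones and so dilute a Visit 4 drift.

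**Conclusion.** The concern holds as a risk of differential reporting bias in the 1-year change in EQ5D and MCSI, of unknown size and direction. Treating-team assessment in one arm and online completion in the other is plain in the text, and no planned analysis can separate mode from treatment. The change in relationship over the year follows from the visit schedule. That it alters answers is inference.

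The error rates of 9-18% (17 v 80) and 11-21% (25 v 60) depend wholly on the assumed 3-5 point drift and on 18 as the SD of change. They show sensitivity and do not estimate the bias. The case for changing the caregiver procedure is the firmest, because the stated reason for interviewing does not reach caregivers. The change should be made, but its absence would not by itself invalidate the study.

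**What to change.** Amend Protocol I.c, III (Study Visits) and Appendix A:

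1. **Caregivers.** Home-visit caregivers self-complete the MCSI and their own EQ5D at every visit on the REDCap survey used by control caregivers, on the team's iPad or by emailed link, with no treating clinician asking. Confirm that this survey contains the MCSI. The usual-care paragraph in III lists the EQ5D but not the MCSI, although I.c and the SAP give caregiver strain for controls.
2. **Patients.** Set each patient's EQ5D mode at Visit 1 and keep it through Visit 4. Where a reader is needed, or is likely to be needed later, the research-team member already at the visit reads the items, not the social worker, nurse or neurologist. Letting patients self-complete until they cannot would be worse: the protocol expects cognitive impairment to increase over time, so some would change mode between baseline and endpoint in this arm only.
3. **Recording and analysis.** Record mode and reader at each visit and flag any unavoidable change of mode. Add a sensitivity analysis to the SAP that excludes those patients, and state the remaining mode difference as a limitation.
4. **Consistency.** Reconcile section III with Appendix A on who administers the scales at Visits 2-4.

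The cost is small: wording changes that use the existing survey, device and staff. The downsides are some caregiver items left blank that an interviewer would have completed, and a mode difference that remains for patients who need a reader.

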##### V.b. Process of Consent

**Home visit subjects:** Subjects will be asked to carefully read the respective IRB-approved Informed Consent Form. The trained research study team member, will obtain consent in a private, distraction-free area in the patient's home. The person obtaining written informed consent from the subject will assess capacity to participate in the research study. It is not practicable to have an individual independent of the study team perform the capacity assessment or obtain informed consent because both are done in the potential subject's home, and both space and funding limit the number of individuals who can practically attend a visit.

Subjects who consent to be contacted about future studies will be notified of potential studies that they are eligible for as studies are available for recruitment. Their consent to participate in the CarePSP study does not apply to other studies. As such, subjects will have to go through the respective consent processes separately. Subjects have the right to refuse participation in any study without consequence to their participation in the registry or their routine patient care. Subjects will be informed about their right to request not to be contacted for specific periods of time or to discontinue active participation in the program, although their data will continue to be stored for future use.

**Usual care subjects:** We have incorporated the components of the informed consent document into the first page of the online survey. Potential subjects must read through the informed consent language on the first page and click a button agreeing to continue. On the next page of the survey, we have incorporated capacity assessment questions to ensure understanding of the consent process. Following correct completion of these questions, the potential subjects are then directed to the actual survey questions.

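### At 12 months control caregivers are reached through the patient, so when a living control who has progressed does not respond, the caregiver's MCSI is likely to be lost too and is carried forward as zero change

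*Protocol*

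**What the plan says.** **Control arm.** Protocol III, Study Visits, Usual care/controls, gives the follow-up route: "Control subjects will be contacted 12 months following the initial survey to complete a follow-up survey". Control subjects with unfinished surveys are then emailed, with as many as three reminders. The caregiver comes in conditionally, "If the control subject indicates that she or he has an available and willing caregiver", and then "the subject will be prompted to have their caregiver complete the caregiver portion of the survey once the subject has completed his portion". Section I.c says that control caregivers will be invited when available, without saying how. To enter, a control needs "Independent access to an internet-connected computer in order to complete online survey" (II.e, usual-care criteria) and a working email address, and must pass capacity questions: "Following correct completion of these questions, the potential subjects are then directed to the actual survey questions" (V.b). No proxy, surrogate, telephone or direct caregiver contact is described for this arm.

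**Home-visit arm.** The survey is given as an interview because expected problems with dexterity and cognition are seen as "limiting the feasibility of completing the online survey unassisted" (III, Home Visit Subjects). A caregiver may consent for a patient who lacks capacity (II.e, V.c). Visits take place wherever the patient is living, and the MCSI is given to the caregiver by the social worker.

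**Analysis.** The SAP (Outcome ascertainment) schedules EQ5D and MCSI at four visits in the program arm and once a year in controls. Under Bivariate analyses, the last EQ5D is carried forward after death or loss, and the last MCSI after loss.

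**The concern.** The protocol expects cognition to worsen in these diseases, "with increasing prevalence of cognitive impairment over time" (II.g). A control who could manage the survey at entry may not manage it a year later. Under the written route, that patient's silence also leaves the caregiver without a prompt, so one non-response can cost two outcomes. The caregiver could often still have answered.

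The two arms are not equally exposed. The same decline in a home-visit patient meets an interviewer, a possible surrogate and a team that travels to the patient, and up to three values may already be on file. A control lost before 12 months has a baseline value and nothing else, so carry-forward turns an unobserved decline into recorded stability. At stake are hypotheses 1 and 2 of section I.a, the between-group comparisons of quality of life and caregiver strain. A different imputation method cannot replace an MCSI that was not collected, so the collection route has to be settled before follow-up.

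**Working it through.** **Inputs from the SAP (Power calculation):** 100 control patients and 60 control caregivers with 20% loss; 20 home-visit patients with 15% loss; VAS difference sought 6.5 to 8.0; baseline VAS mean 37.

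**Assumptions, because the documents give no figure:** unseen VAS decline D among lost, living controls of 6.5, 10, 15 or 20 points; patient loss above 20%; caregiver loss beyond patient loss.

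1. **The plan's own yields.** 100 × 0.80 = 80 control patients; 60 × 0.80 = 48 control caregivers; 20 × 0.85 = 17 home-visit patients. All three match the SAP.

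2. **What the linked route does to caregiver yield.** If a caregiver responds only when the patient has, yield = 60 × (1 − patient loss) × (1 − further caregiver loss).
   - At 20% patient loss and no further loss: 60 × 0.80 × 1.00 = 48.
   - With a further 10%: 60 × 0.80 × 0.90 = 43.2. With a further 20%: 60 × 0.80 × 0.80 = 38.4.
   - At 30%, 40% and 50% patient loss and no further loss: 42, 36 and 30.

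   So, on this route, 48 holds only if every prompted caregiver answers.

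3. **Shift in the control mean change under carry-forward.** Let p be the share lost and m the mean change among responders. The analysed mean is (1 − p) × m + p × 0. The mean with the decline included is (1 − p) × m − p × D. The difference is p × D.
   - p = 0.20: 0.20 × 6.5 = 1.3; 0.20 × 10 = 2.0; 0.20 × 15 = 3.0; 0.20 × 20 = 4.0 points.
   - p = 0.40 (assumed): 2.6, 4.0, 6.0 and 8.0 points.

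   At 20% loss this is between 1.3/8.0 = 16% and 4.0/6.5 = 62% of the difference sought. The top of the range is demanding: a 20-point fall is 20/37 = 54% of the assumed baseline mean. The shift depends on the share lost, not the number enrolled, so it is the same for the protocol's 60 controls as for the SAP's 100.

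4. **Between arms.** Home-visit loss can shift that arm the same way.
   - If its 15% lost have the same D and none of it was recorded, the shift is 0.15 × D and the net distortion is (0.20 − 0.15) × D = 0.05 × D: 0.05 × 6.5 = 0.3 to 0.05 × 20 = 1.0 points.
   - If Visits 2 and 3 had already captured the decline, the net is the full 0.20 × D, or 1.3 to 4.0 points.

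   The four-visit schedule moves the result away from the lower case; how far, the documents do not show.

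5. **MCSI.** The same rule applies, share lost × unseen rise, but the SAP gives no SD or target difference. As an illustration, an unseen rise from the lower edge of moderate strain (20) to that of severe strain (30) is 10 points, and 0.20 × 10 = 2.0 points. In the categorical analysis each lost caregiver stays in the baseline category.

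**The case against.** The strongest reply is that much of the route is inferred from silence. The text describes a prompt; it does not say that the caregiver's form is locked. Section I.c invites caregivers by an unstated path, and there is a second reminder channel: "Control participants and CurePSP support group leaders will be reminded to complete the survey". Nothing forbids a caregiver from helping with entry. This stands against any claim that the caregiver cannot be reached. It does not supply a caregiver address or a direct request, and an informal workaround is not a procedure.

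Several stronger readings are tempting and are not supported:

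- **That the computer and capacity conditions bar controls at 12 months.** Both are stated for entry; neither is said to be repeated. The remark about unassisted completion concerns home-visit patients, so applying it to controls who have progressed is an inference.
- **That decline costs the home-visit arm nothing.** The SAP expects 15% dropout there, and V.c withdraws a patient who loses capacity and has no surrogate.
- **That death is part of the defect.** A patient who has died has no EQ5D by any route, and current caregiving strain ends in either arm. The gap is that no route is described for learning of a death and its date.
- **That the distortion about equals the effect sought.** Removing the worst 20% of controls shifts completers by 0.280/0.80 = 0.35 SD, or 0.35 × 18 = 6.3 points if 18 is taken as the SD of change. That is a one-arm worst case for a completers analysis, which the SAP does not plan. On the same formula 15% home-visit loss gives 0.274 SD, or 0.274 × 18 = 4.9 points, leaving 6.3 − 4.9 = 1.4 net if loss is equally informative in both arms.

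It is also fair to say that the study is declared exploratory (II.a) and that the documents do not show why controls leave.

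**Conclusion.** The point holds as a weakness in data collection. Followed as written, the plan ties the control caregiver's 12-month MCSI to the patient's response, specifies no direct caregiver contact, and then records zero change for both when the patient is silent. The home-visit arm is less exposed to this, not immune.

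The direction is conditional. If lost controls are living decliners, the control course looks milder and the bias runs against the program; the documents do not establish that a real benefit is being hidden. Step 3 gives the size in the control arm, 1.3 to 4.0 VAS points at 20% loss. It rests wholly on assumed declines and is reduced by whatever informative loss occurs in the home-visit arm. The MCSI effect cannot be sized from the documents. No stated sample size changes. The correction is cheap and hard to make after the fact, so it should be made.

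**What to change.** In Protocol III, Study Visits, Usual care/controls:

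- Collect the caregiver's own email address in the baseline survey.
- At 12 months send the caregiver portion (MCSI, caregiver EQ5D, utilization) directly to the caregiver, with its own reminders, whether or not the patient has responded. Name the MCSI there and in Appendix A; neither list of control survey content mentions it, although the SAP relies on it.
- State that the caregiver may help the patient with entry.
- Have the caregiver report the patient's death or facility placement, with its date.

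If a caregiver-proxy patient EQ5D is collected, flag it, keep it out of the primary change score and use it only in a sensitivity analysis. The protocol cites validation of the EQ5D for self-completion and interviewer assistance but does not mention proxy use. Moving from self-report at baseline to proxy at follow-up would put a change of respondent inside the change score.

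Cost: one extra contact field, a REDCap change and an IRB amendment that includes caregiver consent wording. This recovers MCSI most directly. It recovers patient EQ5D only where help with entry is enough, so some patient EQ5D loss will remain for the analysis to handle.
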